11.2.1 Required number of primary endpoint events

The required number of primary endpoint events is 62, as calculated with the formula:

$$events = \frac{(z_{\alpha/2} + z_{\beta})^2}{0.25 \log(HR)}$$

where $z_{\alpha/2}$ and z_{β} are the standard normal percentiles ($\alpha=0.05$, $\beta=0.20$), HR is the expected hazard ratio. A HR of about 0.49 was calculated assuming an exponential model of the survival functions with proportional hazard rates.

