11.2 Sample size calculation

The study sample size calculation is based on the minimum relative difference in the 2-year incidence of syncopal recurrences as compared with placebo (pacemaker OFF).

The 2-year incidence of the primary endpoint in the control group will be assumed equal to the incidence observed in the control arm of the ISSUE 3 trial:⁽¹⁶⁾ this was reported as high as 57%. The ISSUE 3 trial was considered as it selected a large population, had very similar inclusion/exclusion criteria, was recently published.

The BIOSync CLS study is designed to detect a 40% relative reduction of the 2-years incidence of syncopal recurrences (from 57% to 34%) with a statistical Type I and II errors of 0.05 (bilateral) and 0.20, respectively.

Further assumptions:

- Exponential distribution of times to first recurrence
- Accrual time: 2 years
- Total study time: 4 years
- Randomization ratio: 1:1
- Loss incidence: 10% (both arms)

With these assumptions a sample size of 62 patients per study arm (124 in total) is required. This estimate must be further increased by 2%, due to the slight power loss induced by the interim analyses (see section 11.6).

In summary, 128 subjects (64 per study arm) are necessary to reach the study primary objective with the required power.

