11.3 Level of significance and the power of the study

Target study power: 80%

Significance level: 0.05 (bilateral)

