11.6 Provision for interim analyses

Interim analyses will be performed at $t = 0.4$ and 0.7 of the required primary endpoint events or, equivalently, after 25 and 43 endpoint events will be collected.

The final analysis will be performed after the study database has been closed out.

In order to keep the overall type I error at the level of 0.05, two-sided, symmetric O'Brien-Fleming boundaries generated with the Lan-DeMets spending function approach to group-sequential testing will be assumed as early stopping rules for efficacy.

| | | | |
|---------------------|---------|---------|---------|
| t | 0.40 | 0.70 | 1.00 |
| No. endpoint events | 25 | 43 | 62 |
| Z_{up} | 3.3569 | 2.4445 | 2.0005 |
| Z_{low} | -3.3569 | -2.4445 | -2.0005 |
| p | 0.0008 | 0.015 | 0.05 |

Sequential boundaries using the Lan-DeMets method

[figure not shown]

Figure 2. Sequential boundaries during interim analyses. R Software version 3.1.0 (2014-04-10).

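### The printed event formula lacks the square on log(HR), and the 2% interim allowance was added to patients but not to the 62-event target, so power with the interim looks is about 79%, not 80%

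*Protocol*

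**What the plan says.** Protocol 11.2 assumes 2-year syncope recurrence of 57% in the control arm and 34% in the active arm, described as a 40% relative reduction. It sets a two-sided type I error of 0.05 and a type II error of 0.20. On patients it says "With these assumptions a sample size of 62 patients per study arm (124 in total) is required", then "This estimate must be further increased by 2%, due to the slight power loss induced by the interim analyses", and arrives at 128.

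Protocol 11.2.1 turns to events: "The required number of primary endpoint events is 62, as calculated with the formula". The formula has the squared sum of the two normal percentiles over 0.25 log(HR), with no square on the logarithm. The input is described as follows: "A HR of about 0.49 was calculated assuming an exponential model of the survival functions with proportional hazard rates". SAP section 4 repeats the assumptions, the 2% step, the formula and the figure of 62.

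Protocol 11.6 and SAP 7.6 place the interim looks at fractions 0.4 and 0.7 of the required events, that is "after 25 and 43 endpoint events will be collected". Information 1.00 is set at 62 events, and the bounds are 3.3569, 2.4445 and 2.0005. Protocol 11.7 ends the study at 62 events, and 11.3 gives the target power as 80%.

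**The concern.** There are two separate points.

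First, the printed formula cannot return 62. The logarithm of a hazard ratio below 1 is negative, so without the square the result is a negative number of events. A reader who checks the target against the Protocol or SAP cannot reproduce it.

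Second, the plan recognises that interim looks cost power but compensates in a quantity that does not restore it. The primary test is a log-rank test, and the final analysis is tied to an event count. Extra patients make it quicker or more certain that 62 events are reached. They do not add information to an analysis held at 62. The figure of 62 sets both interim looks and the end of the trial, so the 80% power claim depends on it.

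**Working it through.** **Inputs.** Two-sided alpha 0.05 and power 0.80 (Protocol 11.3); 57% and 34% at 2 years, exponential times, 1:1 allocation (11.2); HR about 0.49 (11.2.1); looks and bounds (11.6).

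**1. The formula as printed.** (1.95996 + 0.84162)^2 = 7.8489. With ln 0.49 = -0.71335:

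7.8489 / (0.25 × -0.71335) = -44.0.

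**2. The plan's figure, with the square restored.** (ln 0.49)^2 = 0.50887:

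7.8489 / (0.25 × 0.50887) = 61.7, rounded up to 62.

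This reproduces the stated target, so the square was evidently used in the calculation and lost in print.

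**3. Unrounded hazard ratios.**
- 57% to 34%: HR = ln 0.66 / ln 0.43 = 0.41552 / 0.84397 = 0.4923. Events = 7.8489 / (0.25 × 0.50211) = 62.5.
- Exact 40% reduction, 0.6 × 57% = 34.2%: HR = ln 0.658 / ln 0.43 = 0.4959. Events = 7.8489 / (0.25 × 0.49185) = 63.8.

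**4. Where the 2% went.** 124 × 1.02 = 126.5, and the plan takes 128 (64 per arm). The event target of 62 is the result of step 2 with nothing added.

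**5. Power at 62 events.** With D events the log-rank Z has mean √(D/4) × |ln HR| and variance 1. At information fraction t the mean is multiplied by √t, and looks at fractions s < t have correlation √(s/t). Power without looks is Φ(mean - 1.95996). Power with looks is 1 minus the probability that |Z| stays below 3.3569, 2.4445 and 2.0005 at t = 0.4, 0.7 and 1.0, by trivariate normal integration. √(62/4) = 3.9370.

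| HR | Mean at 62 events | Power, no looks | Power, plan's looks | Events for 80% with looks |
|---|---|---|---|---|
| 0.49 (as stated) | 2.808 | 80.2% | 79.6% | 62.6, so 63 |
| 0.4923 (57% to 34%) | 2.790 | 79.7% | 79.1% | 63.5, so 64 |
| 0.4959 (57% to 34.2%) | 2.761 | 78.8% | 78.2% | 64.8, so 65 |

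The looks cost about 0.6 power points in each row; the rest of the gap comes from rounding the HR. The exact inflation for these bounds is 63.48 / 62.53 = 1.015, so the plan's 2% is about the right size. It was applied to the wrong quantity.

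**6. Type I error.** With mean zero, the same integration gives an overall two-sided alpha of 0.0500.

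**The case against.** The strongest reply is that 62 is correct. It follows from the stated HR once the square is restored, a negative event count shows any reader that the formula is misprinted, and no analysis step uses the formula. All of that stands. A reader might infer from the misprint that the target itself is wrong; the documents do not support that.

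A reader might also infer that the true target is 64. That needs two choices: the unrounded HR of 0.4923 in place of the stated value of about 0.49, and the 2% carried over to events, where the plan applies it to the 124 patients. With the stated HR the same route gives 61.7 × 1.02 = 62.9, or 63; with an exact 40% reduction it gives 63.8 × 1.02 = 65.1, and the exact bounds require 65. No single replacement figure is dictated by the documents.

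It is fair to add that a gap of one or two points is well within the uncertainty of a 57% control rate borrowed from another trial, and that 79.6% rounds to 80%. This limits the importance of the point but does not remove it: power is below 80% at all three hazard ratios, including the stated one. The 80.2% that supports 62 holds only without the interim looks.

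A superscript lost in file conversion cannot be fully excluded. However, both documents show the same form, and both keep the square in the numerator.

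**Conclusion.** The formula is misprinted in both documents and should be corrected, but the error did not reach the figure of 62. The interim allowance was given to patients and not to events, so power at 62 events with the planned looks is 79.6%, 79.1% or 78.2%, depending on which of the plan's inputs is used. The shortfall is about 0.5 to 2 power points. Type I error, the bounds and the choice of test are not affected.

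This rests on proportional hazards, the usual normal approximation for the log-rank statistic, 1:1 allocation, looks at the planned fractions, and 62 events being reached. Whether 128 patients will yield 62 events is a separate question.

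**What to change.** In Protocol 11.2.1 and SAP section 4:
- Print the formula as (z_alpha/2 + z_beta)^2 / (0.25 [log HR]^2).
- Give the HR as 0.492, from 57% and 34%. Note that the formula then gives 62.5, and that 62 events are retained.
- Keep the looks at 25 and 43, and state the power at 62 events with the interim looks as about 79%. Make the power statements in 11.2 and 11.3 agree with this.
- Say that the 2% was added to patients only.

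This is a text correction in two documents, with no change to conduct.

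Raising the target is optional. For 57% to 34%, 64 events with looks at 26 and 45 (0.4 × 64 = 25.6; 0.7 × 64 = 44.8) would give 80.3%. It is not free. Under Protocol 8.8.6 patients leave at 24 months or at a primary endpoint event. At the planned rates the mean 2-year incidence is (57% + 34%) / 2 = 45.5%, so 128 patients give 128 × 0.455 = 58 events before any loss. On the same basis 64 events would need 64 / 0.455, or about 141 patients. Restating the power is the proportionate choice.

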11.3 Level of significance and the power of the study

Target study power: 80%

Significance level: 0.05 (bilateral)

11.4 Expected drop-out rate

Loss incidence: 10% (both arms)

11.5 Pass/fail criteria

The clinical investigation is deemed to be passed if the alternative hypothesis of the primary endpoint is reached.

11.6 Provision for interim analyses

Interim analyses will be performed at $t = 0.4$ and 0.7 of the required primary endpoint events or, equivalently, after 25 and 43 endpoint events will be collected.

The final analysis will be performed after the study database has been closed out.

In order to keep the overall type I error at the level of 0.05, two-sided, symmetric O'Brien-Fleming boundaries generated with the Lan-DeMets spending function approach to group-sequential testing will be assumed as early stopping rules for efficacy.

| | | | |
|---------------------|---------|---------|---------|
| t | 0.40 | 0.70 | 1.00 |
| No. endpoint events | 25 | 43 | 62 |
| Z_{up} | 3.3569 | 2.4445 | 2.0005 |
| Z_{low} | -3.3569 | -2.4445 | -2.0005 |
| p | 0.0008 | 0.015 | 0.05 |

Sequential boundaries using the Lan-DeMets method

[figure not shown]

Figure 2. Sequential boundaries during interim analyses. R Software version 3.1.0 (2014-04-10).

11.7 Termination criteria

With a **sequential study design** the study will stop when a total of 62 primary endpoint events will be collected by the independent agency. The following stopping rules will be used.

11.7.1 Stopping Rules

1. The CCI will be informed monthly by the CRO about the total number of patients who will experience a syncope recurrence (primary endpoint event).
2. When the number of events will reach¹ the predefined limits for interim analyses (40% and 70% of the expected number of events), open queries will be resolved and on site monitoring visits for source data verification will be performed.
3. Unclassified primary endpoint events will be adjudicated (see section 9.9). If available primary endpoint events will be less than the predefined limits for interim analyses after the adjudication process, endpoint point event collection will continue until the required number will be reached.
4. When data set will be cleaned the clinical project manager of the study will inform the appointed independent statistician.
5. The independent statistician will analyze the data according to the Statistical Analysis Plan (SAP). The results will be communicated to the CCI and the sponsor of the study. If the

¹ The number of events may exceed the programmed limit whenever 2 or more events occur at the same time.

primary objective is reached the study stops immediately. The stop date of the study is the date of insertion in the database of the last syncopal recurrence. If the primary objective is not reached the independent statistician will recommend to continue the study until 62 events will be collected. Investigators will not be informed of the results of the interim analyses.

6. After study closure investigators shall complete missing data (apart from the primary events) and close open queries within the following 2 months. Events occurring after the stop date shall not be considered either for primary or for secondary endpoints.

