9.8 Responsibilities of the coordinating clinical investigator and the Steering Committee

The BIOSync CLS clinical study is coordinated by:

Dr. med. [name]
Arrhythmologic Centre
Department of Cardiology
Ospedali del Tigullio
[name]
[name]
Italy

Dr. med. [name] will co-chair the Steering Committee.

The Steering Committee will consist of a local study coordinator in participating country with a sufficient number of active investigational sites.

The CCI ([name]) and the co-CCI ([name]) will be supported in the following activities by the Steering Committee.

The responsibilities of the CCI and the Steering Committee are:

- Development and review of the clinical investigation plan
- Procurement of the central vote of an ethics committee (CCI)
- Performance and progress control of the study
- Continuous assessment of the risk/benefit ratio
- If necessary, decision on premature study termination in consultation with the sponsor
- Contribution to coordination of publication and presentations of study results
- Advising all investigators in medical questions related to the study or study conduction
- Evaluation of potential unexpected adverse events
- Discussion of possible interim results
- Cooperation in writing of the final clinical report

The CCI and the Steering Committee are supported by the clinical study manager and other members of the sponsor.

In addition, the CCI and the Steering Committee members have the same rights and duties as other investigators which are described in the Investigator Agreement.

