21 PUBLICATION POLICY

The first author of the primary publications will be [name], CCI and chairman of the Steering Committee of the BIOSync CLS trial. [name] will be responsible for the preparation of the final study report and of the manuscript of the main paper which must be approved by the Steering Committee before submission for publication

The authors of the primary publication will be 10 investigators (or more, depending on the journal requirements) with the highest scores. A minimum of 5 members of the Steering Committee is warranted. All the members of the Steering Committee will always be cited in any publication of study results.

Each Investigator will receive:

- 1 point for each enrolled subject
- 1 point for each enrolled subject with complete and compliant data set (by source data verification)
- +0.25 points for each compliant and fully reported scheduled in-hospital follow-up
- -0.25 points for each unreported or incompliant (e.g., out of window) scheduled follow-up visit
- -1 point for each underreported or delayed reported Serious Adverse Event, and (Serious) Adverse Device Effect.

The study design may be submitted for publication and the authors of this publication will be the members of the SC. Case reports cannot be submitted for publication by the investigators before the paper on the study design has been published.

Publication of sub-analysis will be submitted after the first main publication and the proposing center will have 2 or more authors. Sub-analysis must be approved by the Steering Committee.

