7.6 Interim analysis

Interim analyses will be performed at t=0.4 and 0.7 of the required primary endpoint events or, equivalently, after 25 and 43 endpoint events will be collected. The final analysis will be performed after the study database has been closed out. In order to keep the overall type I error at the level of 0.05, two-sided, symmetric O'Brien-Fleming boundaries generated with the Lan-DeMets spending function approach to group-sequential testing will be assumed as early stopping rules for efficacy.

t	0.40	0.70	1.00
No. endpoint events	25	43	62
Zup	3.3569	2.4445	2.0005
Z_{low}	-3.3569	-2.4445	-2.0005
р	0.0008	0.015	0.05

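### Interim results go to the coordinating investigator and the sponsor with no limit to a stop/continue message, so trial leadership may hold comparative data while the trial continues

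*Protocol*

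**What the plan says.** Protocol 11.7.1, step 5, has the independent statistician analyse the data at each interim look and then states: "The results will be communicated to the CCI and the sponsor of the study". Only after that does the step separate the two outcomes: stop at once if the objective is reached, or a recommendation to carry on if it is not. The step closes with: "Investigators will not be informed of the results of the interim analyses".

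Protocol 9.8 lists the joint responsibilities of the CCI and the Steering Committee. Three matter here: "Discussion of possible interim results", "Continuous assessment of the risk/benefit ratio" and "If necessary, decision on premature study termination in consultation with the sponsor". The section adds: "In addition, the CCI and the Steering Committee members have the same rights and duties as other investigators". Section 21 describes the same person as "CCI and chairman of the Steering Committee of the BIOSync CLS trial".

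SAP 7.6 gives the timing ("Interim analyses will be performed at t=0.4 and 0.7 of the required primary endpoint events") and the boundaries. It does not say who receives the output or in what form.

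**The concern.** An independent statistician and a bar on informing investigators show that the authors wanted interim results kept away from those who conduct the trial. Step 5 then sends the results to two parties at the centre of conduct, and 9.8 invites a committee of investigators to discuss them.

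The stake is the conduct of the rest of the trial. Under 8.3.2, investigators know each patient's arm. Under 8.3.3, they chase late questionnaires, which are the only source of the primary endpoint. Under 9.6, a change of pacing mode without a primary endpoint event counts as a crossover. Under 9.7, sponsor representatives may help with programming and device interrogation. Under 9.8, the CCI and Steering Committee weigh risk against benefit and can end the study with the sponsor. Anyone in these roles who has seen the interim difference could act on it, knowingly or not, while endpoint data are still coming in.

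**Working it through.** **1. The text.** The communication sentence has no condition and comes before the stop/continue branches, so on its face it covers a look at which the trial continues. Neither document defines the results as a yes/no outcome. The bar on investigators comes later in the same step, and 9.8 treats the CCI and committee members as investigators for rights and duties. Step 5 does not say whether the bar reaches them.

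**2. The plan's own figures.** With HR 0.49, two-sided alpha 0.05, power 80% and 1:1 allocation, events = (1.96 + 0.842)² / (0.25 × ln(0.49)²) = 7.849 / 0.1272 = 61.7, so 62. (The printed formula omits the square on the logarithm; with it, the stated 62 follows.) Then 0.4 × 62 = 24.8 and 0.7 × 62 = 43.4, matching looks at 25 and 43. The printed boundaries give cumulative two-sided crossing probabilities of 0.0008, 0.0147 and 0.0498 under the null, so the efficacy design is sound on this point. I use the two interim looks of 11.6 and SAP 7.6; section 6.3 mentions three.

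**3. Chance that the trial continues after a look.** HR from the planning rates = ln(0.66)/ln(0.43) = 0.492, |ln HR| = 0.709. Expected z = √(events/4) × 0.709.
- Look 1: √6.25 × 0.709 = 1.77 against 3.3569; about 6% cross.
- Look 2: √10.75 × 0.709 = 2.32 against 2.4445; about 45% cross.

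The joint normal calculation at HR 0.49 gives cumulative stopping of 5.7% and 46.4%, so 94% and 54% continue. Under no effect, 99.9% and 98.5% continue.

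**4. Patients still in follow-up.** Simulation of 6,000 trials: 128 patients 1:1, exponential times with 57% and 34% at 2 years, 24-month accrual (11.2; uniform entry assumed), 10% loss read as by 2 years, follow-up capped at 24 months (8.8.6), log-rank test at events 25 and 43. Look 1 falls at month 20.9 and 95.7% of trials continue. Look 2 falls at month 30.1 and 57.1% of all trials continue. Repeats with 3,000 trials gave 95–96% and 55–58%. In continuing trials, by assumed lag from the triggering event to release:

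| | 3 months | 4.5 months | 6 months |
|---|---|---|---|
| Look 1: patients event-free in follow-up | 84.5 | 81.3 | 75.6 |
| Look 1: primary events to come | 24.2 | 21.0 | 18.0 |
| Look 2: patients event-free in follow-up | 49.2 | 43.2 | 37.6 |
| Look 2: primary events to come | 8.9 | 7.1 | 5.6 |

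Capping at the 62-event stop lowers the event counts by 0.3 to 0.4. If the true HR were 0.70 (an assumption), 99.4% and 89.6% of trials would continue.

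**5. What a bare stop/continue message reveals.** The boundary as an approximate observed HR is exp(−z/√(events/4)): exp(−3.3569/2.5) = 0.26 at look 1 and exp(−2.4445/3.279) = 0.47 at look 2. Being told to continue means only that the observed HR lay between about 0.26 and 3.8 (1/0.261), or between about 0.47 and 2.1 (1/0.474).

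**The case against.** **The CCI is named separately.** Step 1 of 11.7.1 gives the CCI monthly event totals, step 5 gives the CCI the results, and only then are investigators excluded. The exclusion can naturally be read as meaning the other investigators. This stands. A reader might infer that step 5 contradicts itself, but the documents do not establish that. The rights-and-duties sentence in 9.8 points the other way without settling it, so the wording is ambiguous.

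**Results may mean only the outcome.** The sentences that follow speak of the objective being reached or not. This stands in part: a reader might infer that estimates by arm are certain to be released, and the text does not say so. But nothing restricts the term either, and 9.8 expects results that can be discussed.

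**Most site investigators are not recipients.** This stands. The counts in the table cover all sites, while the recipients reach patients only through their own practice, the committee's decisions or sponsor support at visits. The counts are upper limits.

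**There are safeguards.** Patients and CRO staff are blinded (8.3.2, 20.2), syncope is assessed only from patient questionnaires (9.6), the boundaries are fixed in advance, and analysis is by ITT. Investigators also already know their own patients' arms and are told of events, so only the pooled comparison is new. These points reduce the risk. They do not cover crossover, retention or a decision to end the study, and ITT does not undo dilution from crossover.

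**The CCI must know in order to stop the trial.** True, but a stop/continue message is enough for that.

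A reader might also infer that comparative data should go to the DSMB. Under 18.11 its members are the adjudicators, who under 9.9 must stay blinded. Whether that works depends on a charter not supplied, so I do not propose it, and I make no finding on adjudicator masking.

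**Conclusion.** The concern holds as a missing limit on interim disclosure: the plan lets the CCI and the sponsor receive, and the Steering Committee discuss, interim results of unspecified content while the trial goes on. This is likely to arise in practice. Under the planning rates about 94–96% of trials pass the first look and 54–58% the second, with at most about 76–85 and 38–49 patients still event-free in follow-up and about 18–24 and 5–9 primary events to come. The percentages rest on the planning rates and printed boundaries; the patient and event counts also rest on the assumed 3 to 6 month lag, uniform accrual and the reading of the 10% loss.

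A reader might take these counts as a measure of bias, or infer that the type I error is inflated. The documents support neither: the size of any bias cannot be computed from them, and the boundaries keep the error rate at about 0.05. The change is worth making because it is cheap and serves the plan's evident intent; the planned analysis does not depend on it.

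**What to change.** In protocol 11.7.1, step 5, replace the sentence on communicating results with: *The independent statistician informs the CCI and the sponsor only whether the boundary was crossed (stop) or not (continue); results by arm are released to them only after the study has stopped.*

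In 9.8, limit the interim-results item to that message. State the same rule in SAP 7.6, so that both documents name the recipients and the content. With this wording it no longer matters for results by arm whether the bar on investigators covers the CCI and committee members.

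The cost is wording in three places, with no change to sample size, boundaries, looks or analysis. The downside is that the CCI, Steering Committee and sponsor do not see interim estimates and must carry out their risk/benefit and termination duties without them while the trial continues.
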